Consortium:	Developmental Synaptopathies Consortium

Double in other a Oite a	Destan Ohildrania Hasnifal	
Participating Sites:	Boston Children's Hospital	
	Cleveland Clinic	
Activation Date:	Stanford University Medical Center June 9, 2017	
Current Status:		
Sample Size:	Open to Enrollment 40 randomized	
Target Enrollment Period:	2 Years	
	Interventional, Phase I/II, Multi-Center	
Study Design: Primary Study Objective:		
Filliary Study Objective.	To evaluate the safety of everolimus compared with placebo in patients with PTEN mutations	
Secondary Study	To evaluate the efficacy of everolimus on neurocognition and	
Objective(s):	behavior in patients with PTEN mutations compared to placebo as	
Objective(3).	measured by standardized, direct and indirect neurocognitive tools	
	and behavioral measures (processing speed/working memory).	
Study Population and Main	Double-Blind Inclusion Criteria	
Eligibility/ Exclusion		
Criteria:	1. Male and female outpatients between 5 and 45 years of age	
	(inclusive);	
	2. Pathogenic PTEN mutation confirmed by clinical genetic	
	testing;	
	3. Participant must be able to complete one of the following three	
	standardized assessments: Conners' Continuous Performance	
	Tasks (CPT-3-mean reaction time), Stanford Binet (SB-5;	
	working memory), or the Purdue Pegboard Test;	
	4. Performance below the age-adjusted population mean on at	
	least one of the above standardized measure: attention (CPT-	
	3, mean reaction time), working memory (SB5), or fine motor	
	skills (Purdue Pegboard Test; either dominant hand, non-	
	dominant hand, or both hands);	
	5. Adequate bone marrow function as shown by:	
	a. platelets ≥ 80,000/mm³	
	b. absolute neutrophil count ≥ 1,000/mm³	
	c. hemoglobin ≥ 9 g/dL 6. Adequate liver function as shown by:	
	a. Total serum bilirubin < 1.5 x ULN	
	b. AST and ALT levels < 2.5 x ULN	
	c. INR ≤ 2	
	7. Adequate renal function: serum creatinine < 1.5 x ULN,	
	8. Signed informed consent obtained prior to any screening	
	procedures;	
	9. Individuals on psychotropic and anti-epileptic medications	
	should maintain a stable dose for at least 2 months prior to the	
	screening visit;	
	10. Negative serum pregnancy test for females at screening and	
	no plans to become pregnant or conceive a child while	
	participating in the study. The effects of mTOR inhibitors on the	
	developing fetus at the doses used in this study are unknown.	
	For this reason, women of child-bearing potential and men	
	must agree to use adequate contraception prior to study entry	
	and for the duration of the study. Estrogen-containing oral	
	contraceptives are not recommended in women enrolled in this	
	study. Abstinence or two effective non-estrogen or barrier	
	methods of contraception (such as condoms + spermicidal foam) must be used;	
	11. No anticipated changes in the frequency and intensity of	
	existing interventions such as behavioral and developmental	
	treatments, in home services, and speech therapy;	
	treatments, in nome services, and special therapy,	

- 12. No planned changes in school placement;
- 13. For individuals under 18 or who are otherwise incapable, there must be an available caregiver who can reliably bring subject to clinic visits and provide trustworthy data

14. Able to communicate fluently in English

Double-Blind Exclusion Criteria

- 15. Patients currently receiving anticancer therapies or who have received anticancer therapies within 4 weeks of the start of Everolimus (including chemotherapy, radiation therapy, antibody based therapy, etc.);
- 16. Known intolerance or hypersensitivity to Everolimus or other rapamycin analogs (e.g. sirolimus, temsirolimus);
- 17. Known impairment of gastrointestinal (GI) function or GI disease that may significantly alter the absorption of oral Everolimus:
- 18. Uncontrolled diabetes mellitus as defined by HbA1c >8% despite adequate therapy. Patients with a known history of impaired fasting glucose or diabetes mellitus (DM) may be included, however blood glucose and antidiabetic treatment must be monitored closely throughout the trial and adjusted as necessary:
- 19. Patient with uncontrolled hyperlipidemia: fasting serum cholesterol > 300 mg/dL OR >7.75 mmol/L AND fasting triglycerides > 2.5 x ULN.
- 20. Patients who have any severe and/or uncontrolled medical or psychiatric conditions (see section 4.6 for additional details)
- 21. Chronic treatment with corticosteroids or other immunosuppressive agents. Topical or inhaled corticosteroids are allowed:
- Known history of or seropositivity for Hepatitis B, Hepatitis C, or HIV:
- 23. Patients who have received live attenuated vaccines within 1 week of start of Everolimus and during the study. Patient should also avoid close contact with others who have received live attenuated vaccines. Examples of live attenuated vaccines include intranasal influenza, measles, mumps, rubella, oral polio, BCG, yellow fever, varicella and TY21a typhoid vaccines;
- 24. Patients who have a history of another primary malignancy, with the exceptions of:
 - a. non-melanoma skin cancer.
 - b. and carcinoma in situ of the cervix, uteri, or breast from which the patient has been disease free for ≥3 years;
- 25. Planned changes to concomitant medications;
- 26. Prior or concomitant therapy with known or possible antimTOR activity, including rapamycin (sirolimus);
- 27. Concomitant therapy with strong inhibitor (e.g., cyclosporine and ketoconazole) or inducer of CYP3A;
- 28. Active infection at time of enrollment;
- 29. Patients with a history of non-compliance to medical regimens or who are considered potentially unreliable or will not be able to complete the entire study;
- 30. Patients who are currently part of or have participated in any clinical investigation with an investigational drug within 1 month prior to dosing;

- 31. Pregnant or nursing (lactating) women;
- 32. Women of child-bearing potential (WOCBP), defined as all women physiologically capable of becoming pregnant, must use highly effective methods of contraception during the study and 8 weeks after. Highly effective contraception methods include:

- a. A combination of any two of the following:
- 33. Use of oral, injected or implanted hormonal non-estrogen containing methods of contraception or;
- 34. Placement of an intrauterine device (IUD) or intrauterine system (IUS);
- 35. Barrier methods of contraception: condom or occlusive cap (diaphragm or cervical/vault caps) with spermicidal foam/gel/film/cream/ vaginal suppository;
- 36. Total abstinence or:
- 37. Male/female sterilization.

Women are considered post-menopausal and not of child-bearing potential if they have had 12 months of natural (spontaneous) amenorrhea with an appropriate clinical profile (e.g. age appropriate, history of vasomotor symptoms) or have had surgical bilateral oophorectomy (with or without hysterectomy) or tubal ligation at least six weeks prior to randomization. In the case of oophorectomy alone, only when the reproductive status of the woman has been confirmed by follow up hormone level assessment is she considered not of child-bearing potential.

- 38. Male patients whose sexual partner(s) are WOCBP who are not willing to use adequate contraception, during the study and for 8 weeks after the end of treatment
- 39. Major surgery, radiation therapy, or stereotactic radio-surgery within previous 4 weeks at time of screening
- 40. Neurosurgery within prior 6 months at time of screening.

Open-Label Inclusion Criteria

- 41. Patients who completed Double-Blind phase of the study and were assigned to the placebo treatment arm;
- 42. Verbal consent (and assent, as appropriate) obtained prior to any open-label phase study procedures.

Treatment	
Agent	Everolimus
Dosage, schedule, route of administration-	4.5mg/m ² /day, to the nearest 2.5mg, orally
Safety Issues-	The safety profile is characterized by manageable adverse events (AEs). These AEs are generally reversible and non-cumulative. Adverse events most frequently observed with everolimus are stomatitis, mouth ulcers, acne, infection, and menstrual irregularities. Adverse events that are also common include: rash, diarrhea, fatigue, asthenia, nausea, peripheral edema, decreased appetite, headache, dysgeusia, epistaxis, mucosal inflammation, pneumonitis, weight decreased, vomiting, pruritus, cough, dyspnea, dry skin, nail disorder, aggression, and pyrexia. Overall, the most frequently observed laboratory abnormalities include: decreased hematology parameters including hemoglobin,

Iymphocytes, platelets, and neutrophils; increased clinical chemistry parameters including cholesterol, triglycerides, glucose, aspartate transaminases, creatinine, alanine transaminases, and bilirubin; and decreased clinical chemistry parameters including phosphate and potassium. The majority of these AEs have been of mild to moderate severity (NCI CTC grade 1-2). Recommendations for dose adjustments, should any of these treatment related adverse events occur, are given in Table 3. Primary Outcome Measures: The primary endpoint will be study drop-out rate due to side effects, comparing everolimus vs. placebo. We will also determine the frequency of adverse events by type and severity. We predict that the rate of adverse events will be no more than 10% higher in the everolimus group compared to placebo but overall severity will be minimal. Secondary Outcome Measures: The main efficacy endpoint will be a neurocognitive composite. This composite will be computed in two ways: 1) an average for working memory (SB-5 working memory), processing speed (CPT mean reaction time) and fine motor (Purdue Pegboard-average of both hands) subtests, and 2) the same average as above excepted weighted 2/3 and an additional average based on all other available neurocognitive testing measures (receptive and expressive language, non-verbal ability, erbal learning, sustained attention, impulsivity, and visuomotor skills, etc.) weighted 1/3. Additional efficacy endpoints will examine the effect of everolimus on overall global clinical improvement, autism symptoms, other behavior problems, and adaptive abilities as measured by validated, standardized instruments including the Clinical Global Impressions-Improvement scale, Autism Diagnostic Observation Schedule — Second Edition (ADOS-2 calibrated severity score), Social Responsiveness Scale-Second Edition (SRS-2), Adult/Child Behavior Checklist (ABCL/CBCL), Wide Range Assessment of Memory and Learning-2 (WRAM-L2) and Vineland Adaptive Behavior Scales, 3 rd Edition (VABS-III).		
Measures: comparing everolimus vs. placebo. We will also determine the frequency of adverse events by type and severity. We predict that the rate of adverse events will be no more than 10% higher in the everolimus group compared to placebo but overall severity will be minimal. Secondary Outcome Measures: The main efficacy endpoint will be a neurocognitive composite. This composite will be computed in two ways: 1) an average for working memory (SB-5 working memory), processing speed (CPT mean reaction time) and fine motor (Purdue Pegboard-average of both hands) subtests, and 2) the same average as above excepted weighted 2/3 and an additional average based on all other available neurocognitive testing measures (receptive and expressive language, non-verbal ability, verbal learning, sustained attention, impulsivity, and visuomotor skills, etc.) weighted 1/3. Additional efficacy endpoints will examine the effect of everolimus on overall global clinical improvement, autism symptoms, other behavior problems, and adaptive abilities as measured by validated, standardized instruments including the Clinical Global Impressions-Improvement scale, Autism Diagnostic Observation Schedule – Second Edition (ADOS-2 calibrated severity score), Social Responsiveness Scale-Second Edition (SRS-2), Adult/Child Behavior Checklist (ABCL/CBCL), Wide Range Assessment of Memory and Learning-2 (WRAM-L2) and Vineland Adaptive Behavior Scales, 3 rd Edition (VABS-III). Statistical Considerations (sample size and analysis plan):		chemistry parameters including cholesterol, triglycerides, glucose, aspartate transaminases, creatinine, alanine transaminases, and bilirubin; and decreased clinical chemistry parameters including phosphate and potassium. The majority of these AEs have been of mild to moderate severity (NCI CTC grade 1-2). Recommendations for dose adjustments, should any of these treatment related adverse events occur, are given in Table 3.
Measures: This composite will be computed in two ways: 1) an average for working memory (SB-5 working memory), processing speed (CPT mean reaction time) and fine motor (Purdue Pegboard-average of both hands) subtests, and 2) the same average as above excepted weighted 2/3 and an additional average based on all other available neurocognitive testing measures (receptive and expressive language, non-verbal ability, verbal learning, sustained attention, impulsivity, and visuomotor skills, etc.) weighted 1/3. Additional efficacy endpoints will examine the effect of everolimus on overall global clinical improvement, autism symptoms, other behavior problems, and adaptive abilities as measured by validated, standardized instruments including the Clinical Global Impressions-Improvement scale, Autism Diagnostic Observation Schedule – Second Edition (ADOS-2 calibrated severity score), Social Responsiveness Scale-Second Edition (SRS-2), Adult/Child Behavior Checklist (ABCL/CBCL), Wide Range Assessment of Memory and Learning-2 (WRAM-L2) and Vineland Adaptive Behavior Scales, 3 rd Edition (VABS-III). Statistical Considerations (sample size and analysis plan):		comparing everolimus vs. placebo. We will also determine the frequency of adverse events by type and severity. We predict that the rate of adverse events will be no more than 10% higher in the everolimus group compared to placebo but overall severity will be
(sample size and analysis plan):	Measures:	This composite will be computed in two ways: 1) an average for working memory (SB-5 working memory), processing speed (CPT mean reaction time) and fine motor (Purdue Pegboard-average of both hands) subtests, and 2) the same average as above excepted weighted 2/3 and an additional average based on all other available neurocognitive testing measures (receptive and expressive language, non-verbal ability, verbal learning, sustained attention, impulsivity, and visuomotor skills, etc.) weighted 1/3. Additional efficacy endpoints will examine the effect of everolimus on overall global clinical improvement, autism symptoms, other behavior problems, and adaptive abilities as measured by validated, standardized instruments including the Clinical Global Impressions-Improvement scale, Autism Diagnostic Observation Schedule – Second Edition (ADOS-2 calibrated severity score), Social Responsiveness Scale-Second Edition (SRS-2), Adult/Child Behavior Checklist (ABCL/CBCL), Wide Range Assessment of Memory and Learning-2 (WRAM-L2) and Vineland Adaptive Behavior Scales, 3 rd Edition (VABS-III).
	(sample size and analysis	See data analysis section of protocol
	plan):	
	Sponsors (federal, state,	National Institutes of Health; Novartis Pharmaceuticals; PTEN
foundation and industry Research Foundation	foundation and industry	Research Foundation
support):	support):	

1. Introduction

This is a Phase I/II 6-month, randomized, double-blind placebo-controlled trial of everolimus in patients, ages 5 to 45 years (inclusive) with a PTEN mutation, with safety and neurocognition as the primary endpoints.

Germline heterozygous phosphatase and tensin homolog (PTEN) gene mutations are associated with a spectrum of clinical disorders characterized by neurocognitive deficits, autism symptomatology, skin lesions, macrocephaly, hamartomatous overgrowth of tissues, and an increased risk of cancers. The neurocognitive and neurobehavioral deficits are associated with very high morbidity, health care cost, and impact on the quality of life of individuals with PTEN and their families. Currently, there are no approved agents for the treatment of these neurocognitive and neurodevelopmental deficits in PTEN.

This protocol addresses a key area of interest: Pharmacological treatments of a well-defined subgroup with autism spectrum disorder. It will leverage an existing investigation that aims at examining the natural history study of individuals with autism and germline heterozygous PTEN mutations (BCH IRB-P00013150: Natural History Study of Individuals with Autism and Germline Heterozygous PTEN Mutations). The purpose of this

phase II pilot study will be to establish short-term safety of everolimus treatment in individuals with germline PTEN mutations and evaluate associated cognitive and behavioral changes in this population to generate plausible hypotheses to be tested in a future Phase III confirmatory trial. This protocol also mirrors a previous clinical trial utilizing everolimus in the tuberous sclerosis population (BCH 10-06-0247 Randomized Double-Blind Phase 2 Trial of RAD001 for Neurocognition in Individuals with Tuberous Sclerosis Complex).

In this investigation, we propose a 6-month randomized, double-blind, multi-site study to evaluate the safety and efficacy of a rapamycin analogue, everolimus, to treat neurocognitive and social deficits in a total of 60 patients (age range 5-45 years) with a PTEN mutation with a maximum of 40 participants randomized to treatment. By maintaining a lower age limit of 5 years, we can ensure a more accurate assessment of cognitive and behavioral outcomes, streamline the neurobehavioral assessment battery, and with minimal loss to outcome measure scope and sensitivity, similar to the strategy we employed in a previous everolimus trial in tuberous-sclerosis complex (TSC) (NCT01289912), performed by PI [name]., Ph.D.

This investigation involves 3 participating sites (Stanford University, site PI: [name].; Cleveland Clinic, site PI: [name].; and Boston Children's Hospital, site PI: [name]., Ph.D.).

2. Objectives and Endpoints

2.1 Primary objective

To evaluate the safety of everolimus compared with placebo in patients with PTEN mutations focusing on NCI CTCAE Grade 3 and 4 adverse events, serious adverse events, and Grade 3 and 4 laboratory toxicities. The primary endpoint will be study drop-out rate due to side effects, comparing everolimus vs. placebo. Based on the published literature and our experience in prior TSC trials we hypothesize that the drop-out rate due to side effects in those receiving everolimus will be similar to those in the placebo group with minimal effect size (< 10% difference). We will also determine the frequency of adverse events by type and severity. We predict that the rate of adverse events will be no more than 10% higher in the everolimus group compared to placebo, but overall severity will be minimal.

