In objective 1, we will examine the safety and tolerability of everolimus by comparing the 1) dropout rates due to side effects, 2) dropout rates for any reason, and the 3) frequency of specific side effects in those receiving everolimus versus placebo. Based on the published literature and our experience in the tuberous sclerosis trial. we predict that the dropout rates due to side effects will be very similar across everolimus and placebo groups (<10% difference). However, we predict that everolimus will cause higher rates of medication-related side effects (≥10% difference) when compared to placebo. We will use chi-square statistics (or Fisher's exact test depending on cell counts) to compare dropout and rates of specific side effects. Statistical significance will be determined using a one-tailed test Type 1 error rate of α=.05, as only increases with everolimus treatment are expected. No false discovery rate correction will be applied because the concern is maximizing sensitivity to any increase in side effect prevalence with everolimus treatment. For dropout rates, we will also compute Kaplan-Meier survival analyses with discontinuation due to side effects or any reason as separate status endpoints. Number of days from baseline to medication discontinuation will be the time variable. Survival analyses are expected to be under-powered due to the generally low dropout rates expected, but these analyses can be useful for describing temporal trends. To ensure any observed group differences are not influenced by other variables or randomization imbalance, cox and logistic regression analysis will also be conducted with and without conditioning on relevant baseline covariates (e.g., demographics, language and cognitive ability, symptom severity).

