17.1 Power Estimation

This is the first study to evaluate the efficacy of everolimus in patients with a PTEN mutation and ASD/DD. As such, analyses will be predominantly descriptive with the intent of generating plausible hypotheses to be tested in a Phase III confirmatory trial. The planned recruitment sample size of 40 was based on three considerations: 1) the expected recruitment potential of the three sites, 2) a desire to ensure sensitivity to any enrichment in side effects or problems with tolerability in everolimus treated patients, and 3) the need for adequate statistical power in examining primary and secondary efficacy outcomes. Assuming an overall dropout rate of approximately 10%, 44 patients will need to be enrolled to get 40 patients with complete trial data. However, following intent to treat procedures, all patients who are randomized, dosed, and for whom baseline data is collected will be included in statistical analyses. Statistical power considerations for each aim/hypothesis are described below. Except for safety analyses, where only everolimus-treated patients would be expected to show enrichment of dropout or side effects, statistical power estimates are based on one-tailed significance tests with Type 1 error rate of α =.05.

Primary Objective- Safety. The planned sample size of 40 is underpowered to detect small differences in dropout rates or side effects between everolimus versus placebo-treated groups. Statistical power will only be adequate if at least a 35% difference in the proportion of dropout/side effects is observed (1- β ≥.81), assuming a one-tailed Type 1 error rate of α =.05. This is equivalent to 1/20 patients experiencing an adverse event/side effect in the placebo arm and 8/20 in the treated arm. Similarly, statistical power of survival analyses will only be fair (1- β ≥.57) if a hazard ratio of 7.5 is observed, equivalent to a 5% dropout rate in the placebo group versus a 30% dropout rate in the everolimus group. However, because the goal is to maintain sensitivity to any potential enrichment in dropout or side effects, any indicator showing a difference of 10% or greater will be considered a meaningful difference and will be reported.

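### The primary safety hypothesis is a drop-out difference under 10 points, but no planned analysis gives a risk difference with a confidence limit, so none can show whether a 10-point excess is excluded

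*Combined protocol and SAP*

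**What the plan says.** Section 2.1 makes drop-out due to side effects the primary endpoint and hypothesises that "the drop-out rate due to side effects in those receiving everolimus will be similar to those in the placebo group with minimal effect size", with a difference below 10%. Section 17 (objective 1) repeats the prediction that "dropout rates due to side effects will be very similar across everolimus and placebo groups".

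For this endpoint Sections 17 and 17.1 plan:

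- A chi-square or Fisher's exact test, one-tailed at 0.05, "as only increases with everolimus treatment are expected".
- Kaplan-Meier analyses of time to discontinuation, with the caution "Survival analyses are expected to be under-powered due to the generally low dropout rates expected".
- Models, to check that differences are not due to other variables or imbalance: "cox and logistic regression analysis will also be conducted with and without conditioning on relevant baseline covariates".
- A reporting rule: "any indicator showing a difference of 10% or greater will be considered a meaningful difference and will be reported".

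On precision, Section 17.1 says "Statistical power will only be adequate if at least a 35% difference in the proportion of dropout/side effects is observed", and equates that with 1/20 against 8/20. The 10% is therefore best read as absolute percentage points. Its survival illustration uses "a 5% dropout rate in the placebo group versus a 30% dropout rate in the everolimus group".

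**The concern.** The hypothesis is that a difference stays under a bound. The planned test asks whether everolimus is worse than placebo by any amount, and failing to find that says nothing about how large an excess remains possible. The flag acts on the observed difference alone and carries no measure of precision. The Cox and logistic models work on hazard- and odds-ratio scales, not on the scale of the bound. With the low drop-out the plan expects, an arm may have no events, and the maximum likelihood ratio is then infinite, zero or undefined.

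Part of the stated purpose (Section 1) is to establish short-term safety before a Phase III trial. A report giving a non-significant p-value and a gap of no more than one patient could be taken as bearing out the under-10% hypothesis when the data leave an excess of 10 points or more open.

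**Working it through.** **Inputs.** 20 per arm and one-sided alpha 0.05 (Section 17.1); bound of 10 points (Sections 2.1 and 17); flag at a 10% difference, which is 2 patients of 20. The 5% placebo rate is the plan's own illustration. Other rates are assumptions. Counts below are everolimus v placebo, and the flag is counted when everolimus has at least two more drop-outs than placebo.

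**The plan's own figure.** Full enumeration of the one-sided Fisher test at true rates of 40% v 5%, 20 per arm, gives power 0.808. This matches the stated .81.

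**Upper limit for the excess.** Newcombe's one-sided 95% limit is d + √[(u₁ − p₁)² + (p₂ − l₂)²]. Here d = p₁ − p₂, arm 1 is everolimus, and l and u are Wilson limits with z = 1.645. For 0/20 the Wilson limits are 0 and 0.1192. For 1/20 they are 0.0112 and 0.1960.

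- 0 v 0: 0 + √(0.1192² + 0²) = 11.9 points
- 1 v 1: 0 + √(0.1460² + 0.0388²) = 15.1 points
- 1 v 0: 0.05 + √(0.1460² + 0²) = 19.6 points
- 0 v 1: −0.05 + √(0.1192² + 0.0388²) = 7.5 points
- 1 v 2, by the same formula: 11.0 points

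Exact unconditional limits are wider: 13.9, 16.0, 21.6 and 8.5 points for the first four. The 0 v 0 value can be checked by hand: 1 − 0.05^(1/20) = 0.139.

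Over all possible counts, the Newcombe limit is below 10 points only when everolimus has fewer drop-outs than placebo. Even that is not always enough, as 1 v 2 shows. Section 17.1 also mentions enrolling 44. With 22 per arm, 0 v 0 gives z²/(n + z²) = 2.706/24.706 = 11.0 points, still above 10.

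**How often each outcome occurs (exact binomial enumeration, 20 per arm).**

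| True rates, everolimus v placebo | Unflagged and Fisher non-significant | Of those, limit ≥10 points | Limit <10 points, all trials |
|---|---|---|---|
| 5% v 5% | 0.874 | 0.612/0.874 = 70% | 0.261 |
| 10% v 10% | 0.792 | 0.557/0.792 = 70% | 0.234 |

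At 15% v 5%, a true 10-point excess, Fisher power is 0.088. The flag is missed with probability 0.402 and raised with probability 1 − 0.402 = 0.598.

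**Zero-event arms.** At 5% in both arms, the chance that at least one arm has no drop-outs is 1 − (1 − 0.95²⁰)² = 0.588. At 10% it is 1 − (1 − 0.90²⁰)² = 0.228. In those trials the ratio models have no finite, non-zero maximum likelihood estimate.

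**The case against.** The strongest reply is that the plan predicts similarity and does not undertake to prove it. Section 17 calls the study exploratory and its analyses predominantly descriptive. The safety analysis is built to pick up harm: it is one-tailed, has no multiplicity correction and flags at 10%. Section 17.1 says openly that 40 patients are too few to detect small differences. The flag does useful work, catching about 60% of trials with true rates of 15% v 5%, against 9% for Fisher's test. Any reader given the counts could compute the interval, which would often only confirm low precision.

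Most of this stands, and it limits the point. A reader might infer that the plan intends to treat a non-significant or unflagged result as proof of similarity. The documents do not support that. Section 17 says what result would support the efficacy hypothesis, but gives no such rule for safety. A reader might also infer that an unflagged null is the likeliest outcome whatever the truth. That holds at equal rates of 5% (0.87), but at 15% v 5% the probability is 0.40.

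What does not stand is that disclosure fills the gap. A power statement describes the chance of detecting a difference before the trial. It does not tell the reader what excess the observed data leave open. A descriptive study is best summarised by an estimate with its precision, and none is specified for the primary endpoint.

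**Conclusion.** The concern holds as a gap between the primary hypothesis and its analysis. The hypothesis is a bound of 10 points, and nothing planned can show whether the bound is met. The planned test is not invalid for its own purpose of detecting an increase, and the documents do not commit the sponsor to a wrong conclusion.

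The gap is material at this sample size. No result with equal counts, or with more drop-outs on everolimus, excludes a 10-point excess. When the arms truly have equal rates, the limit falls below 10 points in only about a quarter of trials (26% at 5%, 23% at 10%).

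These figures assume 20 analysed per arm, absolute percentage points, a one-sided 95% level chosen to match the plan's alpha, and the Newcombe method. Exact limits make the picture slightly worse. The change is worth making before analysis because it concerns the primary endpoint and costs very little.

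**What to change.** In Section 17, prespecify the risk difference in drop-out due to side effects (everolimus minus placebo), with its one-sided 95% upper limit by one named method (Newcombe or exact), as the main summary of the primary endpoint. Report it beside the 10-point flag. Keep the one-tailed test, Kaplan-Meier curves and Cox and logistic models as supportive.

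Add one sentence: a non-significant or unflagged result will not be described as showing a difference below 10% unless the upper limit is below 10 points, and 20 per arm will usually not allow this. The sentence governs wording; it does not add a formal non-inferiority test.

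The cost is one interval in the safety table and one interpretive sentence, with no extra patients or visits. The safety statement becomes more modest.
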